7.0 ADVERSE EVENTS

7.1 Definitions

7.1.1 Adverse Event (AE)

An adverse event (AE) is any untoward medical occurrence (e.g., an abnormal laboratory finding, symptom, or disease temporally associated with the use of a drug) in a patient or clinical investigation subject administered a pharmaceutical product and which does not necessarily have a causal relationship with this treatment. An AE can therefore be any unfavorable and unintended sign (including an abnormal laboratory finding), symptom, or disease temporally associated with the use of a medicinal product, whether or not related to the medicinal product.

Hospitalization for elective surgery or routine clinical procedures that are not the result of an AE (e.g., surgical insertion of central line) need not be considered AEs and should not be recorded as an AE. Disease progression should not be recorded as an AE, unless it is attributable by the investigator to the study therapy.

7.1.2 Suspected Adverse Reaction (SAR)

A suspected adverse reaction (SAR) is any AE for which there is a *reasonable possibility* that the drug is the cause. *Reasonable possibility* means that there is evidence to suggest a causal relationship between the drug and the AE. A suspected adverse reaction implies a lesser degree of certainty about causality than adverse reaction, which means any adverse event caused by a drug.

Causality assessment to a study drug is a medical judgment made in consideration of the following factors: temporal relationship of the AE to study drug exposure, known mechanism of action or side effect profile of study treatment, other recent or concomitant drug exposures, normal clinical course of the disease under investigation, and any other underlying or concurrent medical conditions. Other factors to consider in considering drug as the cause of the AE:

- Single occurrence of an uncommon event known to be strongly associated with drug exposure (e.g., angioedema, hepatic injury, Stevens-Johnson Syndrome)
- One or more occurrences of an event not commonly associated with drug exposure, but otherwise uncommon in the population (e.g., tendon rupture); often more than once occurrence from one or multiple studies would be needed before the sponsor could determine that there is *reasonable possibility* that the drug caused the event.
- An aggregate analysis of specific events observed in a clinical trial that indicates the events occur more frequently in the drug treatment group than in a concurrent or historical control group

7.1.3 Unexpected AE or SAR

An AE or SAR is considered unexpected if the specificity or severity of it is not consistent with the applicable product information (e.g., Investigator's Brochure (IB) for an unapproved investigational product or package insert/summary of product characteristics for an approved product). Unexpected also refers to AEs or SARs that are mentioned in the IB as occurring with a class of drugs or as anticipated from the pharmacological properties of the drug, but are not specifically mentioned as occurring with the particular drug under investigation.

7.1.4 Serious AE or SAR

An AE or SAR is considered serious if, in the view of either the investigator or sponsor, it results in any of the following outcomes:

- Death;
- Is life-threatening (places the subject at immediate risk of death from the event as it occurred);
- Requires inpatient hospitalization (>24 hours) or prolongation of existing hospitalization;*
- Results in congenital anomaly/birth defect;
- Results in a persistent or significant incapacity or substantial disruption of the ability to conduct normal life functions;

- Important medical events that may not result in death, be life-threatening, or require hospitalization may be considered a serious adverse drug experience when, based upon appropriate medical judgment, they may jeopardize the patient or subject and may require medical or surgical intervention to prevent one of the outcomes listed in the definition. For reporting purposes, also consider the occurrences of pregnancy as an event which must be reported as an important medical event.
- All events of possible drug-induced liver injury with hyperbilirubinaemia defined as ALT $\geq 3 \times \text{ULN}$ **and** bilirubin $\geq 2 \times \text{ULN}$ ($>35\%$ direct) (or ALT $\geq 3 \times \text{ULN}$ and INR >1.5 , if INR measured) or termed 'Hy's Law' events (INR measurement is not required and the threshold value stated will not apply to patients receiving anticoagulants). **NOTE:** bilirubin fractionation is performed if testing is available. If testing is unavailable, record presence of detectable urinary bilirubin on dipstick indicating direct bilirubin elevations and suggesting liver injury. If testing is unavailable and a subject meets the criterion of total bilirubin $\geq 2 \times \text{ULN}$, then the event is still reported as an SAE. If INR is obtained, include values on the SAE form. INR elevations >1.5 suggest severe liver injury.
- Any new primary cancers and treatment emergent malignancies (including squamous cell carcinoma and new primary melanoma) with the exception of basal cell carcinoma (BCC). BCC should be reported as an AE or SAE based on the discretion of the investigator.
- Symptomatic LVEF decrease that meets stopping criteria or asymptomatic LVEF decrease that does not recover, as outlined as LVEF guidance (Section 4.4.3.3)
- Retinal pigment epithelial detachment (RPED) or retinal vein occlusion (RVO)

*Hospitalization for anticipated or protocol specified procedures such as administration of chemotherapy, central line insertion, metastasis interventional therapy, resection of primary tumor, or elective surgery, will not be considered serious adverse events.

In addition to the above, cases of fever with rigors or fever with hypotension should be reported as SAEs (regardless of whether or not hospitalization was required).

7.2 Documentation of non-serious AEs or SARs

For non-serious AEs or SARs, documentation must begin from day 1 of study treatment and continue through the 30 day follow-up period after treatment is discontinued.

Collected information should be recorded in the Electronic Case Report Forms (eCRF) for that patient. Please include a description of the event, its severity or toxicity grade, onset and resolved dates (if applicable), and the relationship to the study drug. Documentation should occur at least monthly.

7.3 SAEs or Serious SARs

7.3.1 Timing

After informed consent but prior to initiation of study medications, only SAEs caused by a protocol-mandated intervention will be collected (e.g. SAEs related to invasive procedures such as biopsies, medication washout, or no treatment run-in).

For any other experience or condition that meets the definition of an SAE or a serious SAR, recording of the event must begin from day 1 of study treatment and continue through the 30 day follow-up period after treatment is discontinued.

7.3.2 Documentation and Notification

These events (SAEs or Serious SARs) must be recorded in the SAE console within Oncore™ for that patient within 24 hours of learning of its occurrence. For Affiliate sites, an email must also be sent to the NCCN Study Coordinator indicating that an SAE or Serious SAR has been entered into Oncore (email contact will be provided at study start-up).

7.3.3 Reporting

IRB Reporting Requirements:

UNC:

The UNC IRB will be notified of all SAEs that qualify as an Unanticipated Problem as per the UNC IRB Policies using the IRB's web-based reporting system within 7 days of the Investigator becoming aware of the problem. Please note, these events must be reported to the sponsor within 24 hours of learning of the occurrence.

Affiliate sites:

- For affiliate sites using a local IRB of record, please submit adverse events per local IRB policy.
- For affiliate sites relying on the UNC-IRB, the UNC IRB will be notified of all SAEs that qualify as an Unanticipated Problem as per the UNC IRB Policies using the IRB's web-based reporting system within 7 days of the Investigator becoming aware of the problem. Please note, these events must be reported to the sponsor within 24 hours of learning of the occurrence.

Novartis Reporting Requirements:

The principal investigator has the obligation to report all serious adverse events to the FDA (if applicable), IRB, and Novartis Pharmaceuticals Drug Safety and Epidemiology Department (DS&E) (*For patients taking Novartis drugs*).

All events reported to the FDA by the investigator are to be filed utilizing the Form FDA 3500A (MedWatch Form), if applicable

To ensure patient safety, every SAE, regardless of suspected causality, occurring after the patient has provided informed consent and until at least 30 days after the patient has stopped study treatment must be reported to Novartis within 24 hours of learning of its occurrence. Information about all SAEs is collected and recorded on a Serious Adverse Event Report Form. The investigator must assess and record the relationship of each SAE to each specific study treatment (if there is more than one study treatment), complete the SAE Report Form in English, and **send the completed, signed form along with the Novartis provided fax cover sheet to the Novartis Oncology Drug Safety and Epidemiology (DS&E) department by fax ([contact]) within 24 hours.**

Any additional information for the SAE including complications, progression of the initial SAE, and recurrent episodes must be reported as follow-up to the original episode within 24 hours of the investigator receiving the follow-up information. An SAE occurring at a different time interval or otherwise considered completely unrelated to a previously reported one should be reported separately as a new event.

Any SAEs experienced after the 30 day safety evaluation follow-up period should only be reported to Novartis if the investigator suspects a causal relationship to the study treatment.

Follow-up information is submitted in the same way as the original SAE Report. Each re-occurrence, complication, or progression of the original event should be reported as a follow-up to that event regardless of when it occurs. The follow-up information should describe whether the event has resolved or continues, if and how it was treated, whether the blind was broken or not, and whether the patient continued or withdrew from study participation.

If the SAE is not previously documented in the Investigator's Brochure or Package Insert (new occurrence) and is thought to be related to the Novartis study treatment, an oncology Novartis Drug Safety and Epidemiology (DS&E) department associate may urgently require further information from the investigator for Health Authority reporting. Novartis may need to issue an Investigator Notification (IN), to inform all investigators involved in any study with the same drug that this SAE has been reported. Suspected Unexpected Serious Adverse Reactions (SUSARs) will be collected and reported to the competent authorities and relevant ethics committees in accordance with Directive 2001/20/EC or as per national regulatory requirements in participating countries.

Pregnancies

To ensure patient safety, each pregnancy occurring while the patient is on study treatment must be reported to Novartis within 24 hours of learning of its occurrence. The pregnancy should be followed up to determine outcome, including spontaneous or voluntary termination, details of the birth, and the presence or absence of any birth defects, congenital abnormalities, or maternal and/or newborn complications.

Pregnancy should be reported by the investigator to the Novartis Oncology Drug Safety and Epidemiology Department (DS&E) by fax (**[contact]**). Pregnancy follow-up should include an assessment of the possible relationship to the study treatment and any pregnancy outcome. Any SAE experienced during pregnancy must be reported on the SAE Report Form.

Pregnancy outcomes must be collected for the female partners of any males who took study treatment in this study. Consent to report information regarding these pregnancy outcomes should be obtained from the mother.

FDA Expedited Reporting requirements for studies conducted under an IND:

A sponsor must report any suspected adverse reaction that is both serious and unexpected and related to the cellular product to the FDA. The sponsor must report an adverse event as a suspected adverse reaction only if there is evidence to suggest a causal relationship between the cellular product and the adverse event, such as:

- A single occurrence of an event that is uncommon and known to be strongly associated with cell infusion exposure (e.g., angioedema, hepatic injury, Stevens-Johnson Syndrome);
- One or more occurrences of an event that is not commonly associated with cellular product exposure, but is otherwise uncommon in the population exposed to the cellular product (e.g. tendon rupture);
- An aggregate analysis of specific events observed in a clinical trial (such as known consequences of underlying disease or condition under investigation or other events that commonly occur in the study population independent of cellular product therapy) that indicates those events occur more frequently in the cell infusion treatment group than in a concurrent or historical control group.

The sponsor must submit each IND safety report on a MedWatch form. Each notification to FDA must bear prominent identification of its contents, i.e., “IND Safety Report,” and must be transmitted to the review division that has the responsibility for review of the IND. For this study, the review division is the Center for Drug Evaluation and Research. In each IND safety report, the sponsor must identify all IND safety reports previously submitted to FDA concerning a similar suspected adverse reaction, and must analyze the significance of the suspected adverse reaction in light of previous, similar reports or any other relevant information.

Timing

FDA must be notified of potential serious risks within 15 calendar days after the sponsor determines the event requires reporting. FDA must be notified of unexpected fatal or life-threatening suspected adverse reactions as soon as possible but in no case later than 7 calendar days after the sponsor's initial receipt of the information. The sponsor must be notified of the SAE by the investigator within 24 hours of the event. If the results of a sponsor's investigation show that an adverse event not initially determined to be reportable is reportable, the sponsor must report such suspected adverse reaction in an IND safety report as soon as possible, but in no case later than 15 calendar days after the determination is made.

Follow-up

The sponsor must promptly investigate all safety information it receives. Relevant follow-up information to an IND safety report must be submitted as soon as the information is available and must be identified as such, i.e., "Follow-up IND Safety Report." Additionally, upon request from FDA, the sponsor must submit to FDA any additional data or information that the agency deems necessary, as soon as possible, but in no case later than 15 calendar days after receiving the request.

Notification of Investigators

The sponsor must notify all participating investigators (i.e., all investigators to whom the sponsor is providing cell infusion under its INDs or under any investigator's IND) in an IND safety report of potential serious risks, from clinical trials or any other source, as soon as possible, but in no case later than 15 calendar days after the sponsor determines that the information qualifies for reporting.

Process

If the sponsor deems that an event is both a serious adverse reaction (SAR) AND unexpected, it must also (in addition to Oncore) be recorded on the MedWatch Form 3500A as per 21 CFR 312.32. Unexpected adverse events or adverse reaction refers to an event or reaction that is not listed in the Investigator's Brochure or is not listed at the specificity or severity that has been observed; or if an investigator's brochure is not required or available, is not consistent with the risk information described in the general investigation plan or elsewhere in the current IND application.

The MedWatch form should be submitted on MedWatch by the study coordinator.

The MedWatch 3500a form can be accessed at:
<http://www.fda.gov/Safety/MedWatch/HowToReport/DownloadForms/default.htm>.

(Please be sure and access form 3500a, and not form 3500).

The MedWatch form should also be sent to the UNC Regulatory Associate and the IND Specialist within 48 hours of the sponsor being aware of the event. The Regulatory Associate with the aid of the IND Specialist will submit the IND Safety Report via IND serial submission to the FDA review division.

Additional Reporting Requirements

The following additional items must be reported via IND safety report:

- *Findings from other studies.* The sponsor must report any findings from epidemiological studies, pooled analysis of multiple studies, or clinical studies, whether or not conducted under an IND, and whether or not conducted by the sponsor, that suggest a significant risk to humans exposed to the cell infusion.
- *Findings from animal or in vitro testing.* The sponsor must report any findings from animal or *in vitro* testing, whether or not conducted by the sponsor, that suggest a significant risk in humans exposed to the cell infusion, such as reports of mutagenicity, teratogenicity, or carcinogenicity, or reports of significant organ toxicity t or near the expected human exposure.
- *Increased rate of occurrence of serious suspected adverse reactions.*

Additional Guidance

Please refer to 21CFR312.32 and “Guidance for Industry and Investigators: Safety Reporting Requirements for INDs and BA/BE Studies” for additional information and reporting requirements. All IND Safety Reports will be submitted in accordance with these regulations/guidances.

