3.0 PATIENT ELIGIBILITY

3.1 Main Study Inclusion Criteria

Subject must meet all of the inclusion criteria to participate in this study:

- 3.1.1 Age ≥ 18 years
- 3.1.2 Signed written informed consent
- 3.1.3 Histologically confirmed V600E or V600K BRAF mutant melanoma
- 3.1.4 Unresectable Stage III/IV melanoma
- 3.1.5 ECOG PS 0-2
- 3.1.6 Normal organ function as defined by the following:
- Absolute neutrophil count $\geq 1.2 \times 10^9/L$
 - Hemoglobin ≥ 9 g/dL, platelets $\geq 75 \times 10^9/L$
 - PT/INR and PTT $\leq 1.5 \times$ ULN (Note: subjects receiving anticoagulation treatment may enroll with INR established within the therapeutic range prior to D1 of treatment)
 - Albumin ≥ 2.5 g/dL
 - Total bilirubin $\leq 1.5 \times$ ULN (patients with elevated bilirubin due to Gilbert's disease will not be excluded)
 - AST and ALT $\leq 2.5 \times$ ULN
 - CrCl ≥ 50 mL/min per Cockcroft-Gault
- 3.1.7 Prior anti-cancer treatment related toxicities except alopecia and lab values as outlined in section 3.1.6 must be \leq Grade 1 as per NCI CTCAEv4.
- 3.1.8 Willing to undergo biopsy for research purposes only (see section 6.6). **Note:** If possible, the pre-treatment biopsy should be performed after all other eligibility criteria are confirmed. Please also see the note in section 6.9.3 regarding assessment of biopsied lesions per RECIST v1.1.
- 3.1.9 Females of child-bearing potential: willing to use two forms of effective contraception, and to continue use for 16 weeks (4 months) post last dose of study medication. Effective contraception is defined as:
- An intrauterine device with a documented failure rate of less than 1% per year.
 - Male partner sterilization prior to the female subject's entry, and this male is the sole sexual partner for that female.
 - Complete abstinence from sexual intercourse for 14 days prior to enrollment, throughout study treatment, and for at least 4 months after the last dose of study treatment. Abstinence is only acceptable when in line with the preferred and usual lifestyle of the subject. Periodic abstinence (e.g. calendar, ovulation, symptothermal, post-ovulation methods, etc) and withdrawal are not acceptable methods of contraception.

- Double-barrier contraception: condom and occlusive cap (diaphragm or cervical/vault caps) with a vaginal spermicidal agent (foam/gel/cream/suppository).

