Note: Hormonal-based methods (e.g., oral contraceptives) are not permitted as contraception due to potential drug-drug interactions with dabrafenib. Female subjects who are lactating must discontinue nursing prior to the first dose of study treatment and must refrain from nursing throughout the treatment period and for 4 months following the last dose of study treatment.

Females of non-childbearing potential are those who are postmenopausal (defined as greater than 1 year without menses with an appropriate clinical profile, e.g., age appropriate, >45 years in the absence of hormone-replacement therapy (HRT). In questionable cases, the subject must have a follicle-stimulating hormone (FSH) value >40 mIU/mL and an estradiol value <40 pg/mL (<140 pmol/L); or who have had a bilateral tubal ligation or tubal occlusion, bilateral oophorectomy or hysterectomy. Men with a female partner of childbearing potential must have either had a prior vasectomy or agree to use effective contraception as described from D1 of treatment, throughout the treatment period, and for 16 weeks after the last dose of study treatment. If a subject becomes pregnant during the treatment period of the study, the study treatments should be stopped immediately.

- 3.1.10** In women of child-bearing potential, negative serum pregnancy test within 48 hours prior to day 1 of study treatment and agree to use effective contraception as outlined in section 3.1.9
- 3.1.11** Measurable disease as defined by RECIST v1.1
- 3.1.12** Able to swallow and retain oral medication
- 3.1.13** Left ventricular ejection fraction by ECHO \geq institutional lower limit of normal
- Patients with a history of hypertension MUST have hypertension adequately controlled (BP < 140/90) with appropriate anti-hypertensive therapy or diet prior to study entry. Note:** To be eligible a subject must have an average of BP below 140/90 based on 3 separate measures. If the subject has a record of BP recordings taken at home, \leq 20% of BPs taken should have numbers > 140/90.

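### The unconditional duty to report a patient's own pregnancy ends 30 days after treatment at the latest, while section 3.1.9 requires contraception for 16 weeks after the last dose

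*Combined protocol and SAP*

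**What the plan says.** Three sets of rules bear on this point.

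**Pregnancy rule.** Under Pregnancies in section 7.3.3, "each pregnancy occurring while the patient is on study treatment must be reported to Novartis within 24 hours of learning of its occurrence". The next sentence requires the pregnancy to be followed to its outcome, so that duty attaches to the same on-treatment pregnancies. A separate sentence requires outcomes to be collected for female partners of treated men, with no time limit.

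**SAE route.** Section 7.1.4, within the definition of a serious event, adds: "For reporting purposes, also consider the occurrences of pregnancy as an event which must be reported as an important medical event". Under 7.3.1, "recording of the event must begin from day 1 of study treatment and continue through the 30 day follow-up period after treatment is discontinued". Under 7.3.3, every SAE from consent "until at least 30 days after the patient has stopped study treatment must be reported to Novartis within 24 hours of learning of its occurrence". Beyond that point, "Any SAEs experienced after the 30 day safety evaluation follow-up period should only be reported to Novartis if the investigator suspects a causal relationship".

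**Contraception periods.** Section 3.1.9 requires women of child-bearing potential to use contraception and "to continue use for 16 weeks (4 months) post last dose of study medication". For men with a partner of child-bearing potential it applies "for 16 weeks after the last dose of study treatment". Section 5.1.5 (trametinib) gives 4 months for women. Section 5.2.8 (dabrafenib, reproductive effects) gives 4 weeks for women and 16 weeks for men. Sections 5.1.5 and 5.2.8 both report teratogenic effects in animals.

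**The concern.** The protocol asks patients to avoid conception for months after the last dose of two drugs it describes as teratogenic in animals, but its unconditional duty to report a pregnancy ends much earlier. A site that follows the text exactly could learn of a pregnancy in, say, week 10 after the last dose and have no clear obligation to report it or follow it to outcome.

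The conditional route after day 30 suits pregnancy poorly. It asks whether study treatment caused the event. The safety question is fetal exposure, not whether a drug caused conception, so an uncomplicated pregnancy would probably not meet that test. A birth defect is itself serious under 7.1.4, but nothing in the text obliges anyone to follow such a pregnancy far enough to learn of one.

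What is at stake is fetal-safety information. No efficacy endpoint, sample size or correlative analysis depends on it.

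**Working it through.** The plan gives no figure to reproduce here. The check compares the length of the post-treatment reporting window with the length of the contraception period.

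**Inputs**
- Unconditional reporting after treatment under the Pregnancies paragraph alone: 0 days (7.3.3).
- Unconditional reporting after treatment with the SAE route: R = 30 days (7.1.4 with 7.3.1 and 7.3.3).
- Contraception period W: 16 weeks = 16 × 7 = 112 days (3.1.9, both sexes; 5.2.8, men); 4 months = 365.25 / 3 ≈ 122 days (5.1.5); 4 weeks = 28 days (5.2.8, women).

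**Formula.** Days without an unconditional duty = max(0, W − R). Share of the period = max(0, W − R) / W.

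| Contraception period | W (days) | Covered by 30 days | Uncovered days | Uncovered share |
|---|---|---|---|---|
| 16 weeks (3.1.9) | 112 | 30/112 = 27% | 112 − 30 = 82 (days 31 to 112) | 82/112 = 73% |
| 4 months (5.1.5) | about 122 | 30/122 = 25% | about 92 | 92/122 = 75% |
| 4 weeks (5.2.8, women) | 28 | all | 0 | 0% |

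**Sensitivity.** The end-of-treatment visit is at 30 days, plus or minus 7 (sections 6.1 and 6.5). If reporting in practice ran to day 37, the uncovered part of 16 weeks would be 112 − 37 = 75 days, or 75/112 = 67%.

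**What the phrase at least 30 days adds.** In 7.3.3 it sets a minimum for SAE reporting. The later sentence on events after the 30-day period makes those reportable only on suspicion of causality, and 7.3.1 ends recording at 30 days. Read together, they leave no unconditional duty after day 30.

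**What cannot be computed.** The documents give no pregnancy rate and no timing of conceptions. The 73% is a share of calendar time. It would equal a share of pregnancies only if conceptions fell evenly over the 112 days, which nothing in the documents supports or excludes.

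**The case against.** The case against giving this much weight has several parts.

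- **Reporting does not stop at the last dose.** A reader of 7.3.3 alone might infer that pregnancies are reportable only on treatment, leaving all 112 days uncovered. The documents do not support that: 7.1.4 makes pregnancy reportable without an on-treatment limit, and the SAE rules carry it to day 30. This stands.
- **After day 30 there is still a route.** Events with suspected causality remain reportable, and a congenital anomaly is itself serious. This stands, but the route is conditional and its test does not fit an uncomplicated pregnancy.
- **Partner pregnancies.** A reader might infer the same gap for partners. The partner sentence has no time limit, so outcomes must be collected whenever the pregnancy occurs. Inserting a 16-week window there could narrow the duty. This stands.
- **The 16 weeks is a contraception period.** The protocol never calls it a period of fetal risk or of reporting, and its own figures differ. Against the 4 weeks in 5.2.8, the 30-day route leaves nothing uncovered. This stands as a reason to reconcile the passages. It does not remove the mismatch with 3.1.9, which is the eligibility rule patients must meet.
- **Few events are likely.** The study plans 20 patients. Women of child-bearing potential must use contraception and have a negative serum test within 48 hours before day 1. This limits the expected number of reports, but does not make the reporting rule coherent.

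**Conclusion.** The concern holds as a mismatch between stated rules. Against the 16-week period in 3.1.9, days 31 to 112 (82 of 112 days, 73%) carry no unconditional duty to report a patient's own pregnancy. With the 4 months in 5.1.5 the figure is about 92 of 122 days (75%); with the 4 weeks in 5.2.8 it is zero. The size therefore depends on which contraception period the protocol adopts, and on reading 7.1.4 as bringing pregnancy under the SAE timing rules.

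A reader might go further and infer that most exposed post-treatment pregnancies would go unreported. The documents do not show this: they give no pregnancy rate, the percentage describes time, and reporting on suspected causality continues after day 30. The finding concerns patients' own pregnancies, not those of partners.

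It is worth correcting because the rule as written falls short of the protocol's own precaution and the correction is cheap.

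**What to change.** 1. Reconcile the post-treatment contraception periods in 3.1.9, 5.1.5 and 5.2.8, so that the protocol states one position for women and one for men. Which period is right is not a question for this review.
2. In 7.3.3, under Pregnancies, extend the 24-hour report and the outcome follow-up to any patient pregnancy that occurs on treatment or within the post-treatment contraception period so adopted. State the same window in 7.1.4, and say there that the 30-day limit in 7.3.1 and the causality condition in 7.3.3 do not apply to pregnancy within it.
3. Leave the partner-pregnancy outcome duty no narrower than it is now.

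**Cost.** A few sentences in the protocol, a line in the site safety instructions, and probably a small number of extra reports. Some outcome follow-up would run past the present schedule. Sections 4.7 and 6.6 keep dermatologic contact for 6 months after dabrafenib, which spans the 16 weeks, but those exams may be done by a local physician, and a pregnancy conceived near week 16 would continue beyond that contact. Sites would need a way to obtain the outcome. Sample size and the primary analysis do not change.
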